## **6.1 Information to be collected on screening failures**

All subjects who sign the informed consent but discontinue prior to randomization at Visit 2 are considered to be screen failures.

If a subject discontinues prior to randomization, the IRT provider must be notified within 5 days, and the reason for the subject not being randomized will be entered on the Screening Phase Disposition eCRF. The Screening visit date, the Demography eCRF, the Informed Consent eCRF, the Inclusion/Exclusion eCRF, and the subject rescreening eCRF must be completed. The AE eCRF should be completed for any SAEs that occurred during the screening period. Adverse events that are not SAEs will be followed by the investigator and collected only in the source data. The Death eCRF should be completed in the case of a death during the screening period. The withdrawal of consent eCRF must be completed if consent was withdrawn during the screening period before the subject was randomized.

For all subjects who sign the informed consent and entered into the next period of the study, all AEs **occurring after the informed consent is signed** will be recorded on the AE eCRF.

Investigators will have the discretion to record abnormal test findings on the medical history CRF whenever in their judgment, the test abnormality occurred prior to the informed consent signature.

## **6.2 Subject demographics/other baseline characteristics**

All Baseline assessments should be performed prior to first study treatment administration. These may be in the screening period (e.g. demographics) or at the Randomization Visit (e.g. PROs), depending on the assessment.

### **6.2.1 Demographics**

Data to be collected on all patients include: year of birth, age, sex, race, ethnicity, and child-bearing potential (for females).

### **6.2.2 Psoriasis medical history / Previous psoriasis therapy**

Disease history will be collected at the screening visit. The information to be collected and entered in the Psoriasis History eCRF and Prior Psoriasis Therapies eCRF includes the following:

- The date of first diagnosis of plaque psoriasis (by a physician)
- The previous treatments of psoriasis (including previous use systemic therapies, biologic therapies, as well as phototherapy and/or photo chemotherapy or topical use) and the reason for discontinuation of each therapy
- The presence of psoriatic arthritis and the date of first diagnosis (by a physician)

### **6.2.3 Relevant medical history / current medical conditions**

Relevant medical history and current medical conditions, not including psoriasis or psoriatic arthritis, prior to signing of the informed consent will be recorded in the Medical History eCRF. Whenever possible, diagnoses and not symptoms will be recorded.

Significant findings that are observed after the subject has signed the informed consent form and that meet the definition of an AE must be recorded in the AE eCRF.

Investigators will have the discretion to record abnormal test findings on the medical history CRF whenever in their judgment, the test abnormality occurred prior to the informed consent signature.

#### **6.2.4 Chest X-ray (optional)**

Chest X-ray is an optional assessment which can be performed in screening at the discretion of the investigator, if warranted for the subject. This is aimed to detect ongoing infection and particularly tuberculosis or malignancy.

A chest X-ray (or chest MRI at pre specified sites) must only be done after it is fairly certain that the subject meets the other inclusion/exclusion criteria, in order to minimize unnecessary exposure to X-ray radiation for subjects.

If the chest X-ray or MRI evaluated by a qualified physician shows evidence of ongoing infections or malignancy and the subject was not treated subsequent to the X-ray (or MRI), the subject will not be eligible to enter the study.

#### **6.2.5 Determination of Tuberculosis status**

Determination of tuberculosis (TB) status will be required before administration of study treatment and should be performed as defined by local guidelines. TB status must be determined by medical history, signs, symptoms and TB testing (QuantiFERON-TB Gold assay). Any significant findings will be recorded in the TB assessment eCRF and the Medical History eCRF, as necessary.

##### **QuantiFERON TB-Gold In-Tube assay**

A QuantiFERON® TB-Gold In-Tube assay (QFT) will be performed to assess the TB status at screening for all subjects. This test will only be used to determine subject's eligibility for the trial. The test will be used to screen the subject population for latent tuberculosis infection ([Doherty 2008](#)).

This blood-based assay is specific for *Mycobacterium tuberculosis* and is not influenced by previous *Bacillus Calmette-Guérin* vaccination or exposure to other *Mycobacteria* species. This test, in contrast to the purified protein derivative (PPD) skin test, is also insensitive to a booster effect since the subject is not exposed to the vaccine. The assay measures the production of interferon-gamma and presents it relative to a negative and a positive control sample. Further information is available in [Manuel and Kumar \(2008\)](#).

The QuantiFERON®-TB Gold assay test will be supplied by the central laboratory. Details on the collection, shipment of samples and reporting of results by the central laboratory are provided to investigators in the laboratory manual.

[figure not shown]
Refer to [Figure 6-1](#) for guidance on subject eligibility with respect to TB testing. The results of a workup for a subject with a positive or indeterminate test must be recorded on the Tuberculosis assessment eCRF.

- If the test result is **negative**, the subject may be randomized.

- If the test result is **positive**, the investigator should perform workup for the test result as per local procedures. If a TB workup was conducted prior to the screening the subject, results of the workup can be used to assess eligibility if the workup was conducted within 12 weeks prior to randomization.
- Subjects' positive for latent TB per workup may be randomized to the trial if sufficient treatment has been initiated according to local routine clinical practice and will be maintained for the prescribed duration. Subjects positive for active TB per workup are not eligible for the study. Subjects negative for TB (no signs of latent or active TB) per workup may be randomized to the trial.
- If the test result is **indeterminate**, the investigator **may repeat the test once or may proceed directly to perform workup** for the test result as per local procedures. This action is at the discretion of the investigator. If a TB workup was conducted prior to the screening the subject, results of the workup can be used to assess eligibility if the workup was conducted within 12 weeks prior to randomization.
- If the second test is negative, the subject may be randomized.
- If the second test is positive, the investigator should perform workup as per local guidelines. Subjects' positive for **latent** TB per workup may be randomized to the trial if sufficient treatment has been initiated according to local routine clinical practice and will be maintained for the prescribed duration. Subjects **positive for active** TB per workup **are not eligible** for the study. Subjects negative for TB per workup (no signs of latent or active TB) may be randomized to the trial.
- If the second test is again indeterminate, the investigator should perform follow-up for the test result as per local procedures. Subjects tested positive for **latent** TB per workup may be randomized to the trial if sufficient treatment has been initiated according to local routine clinical practice. Subjects positive for **active** TB per workup are not eligible for the study. Subjects negative for TB per workup (no signs of latent or active TB) may be randomized to the trial if the workup was conducted 12 within weeks prior to randomization.

If eligibility is being assessed with only 1 test result and a TB workup (i.e., no second TB test will be performed), the TB test to assess eligibility must have been done via the central laboratory for the study within the screening period (within 4 weeks prior to randomization) and TB workup will only be considered if it was completed **within 12 weeks** prior to randomization. Subjects' positive for latent TB per workup may be randomized to the trial if sufficient treatment has been initiated according to local routine clinical practice and will be maintained for the prescribed duration. Subjects positive for active TB per workup are not eligible for the study. Subjects negative for TB per workup (no signs of latent or active TB) may be randomized to the trial.

**Figure 6-1** Tuberculosis screening flowchart

The subject will not be eligible for randomization if "active tuberculosis is present" or if "latent tuberculosis is present and is untreated as per local guidelines."

\* If the first Quantiferon® TB-Gold In-Tube test (QFT) is indeterminate, the investigator may choose to perform a second QFT or refer the subject for tuberculosis workup per local guidelines.

\*\* If the result of any QFT is "positive" or the results of 2 sequential QFTs are "indeterminate", the subject must be referred to have a tuberculosis workup per local guidelines (if no workup within 12 weeks prior to randomization is available).

### **6.2.6 Other baseline characteristics**

Baseline characteristic data to be collected on all subjects include (all labs are central except where indicated):

ECG, vital signs; hematology; clinical chemistry; local urinalysis; past medical history record of HIV, hepatitis B or hepatitis C status; [REDACTED] PASI; IGA mod 2011; cDLQI. A serum pregnancy test will be performed for females of child bearing potential or of at least 12 years of age.

### **6.3 Treatment exposure and compliance**

All doses of study treatment administration will be recorded on the appropriate Dosage Administration Record eCRF page (visit specific and summary pages).

Information on drug dispensing, administration, accountability will be collected in drug accountability logs and other documents as appropriate. For drug administrations at home subject will record relevant information at home which will then be transcribed at the corresponding documents at site including Dosage Administration Record eCRF page (see also [Section 5.5](#)).

Compliance will also be assessed and confirmed by field monitor via drug accountability logs and via info documentation and information provided by IRT and by the qualified site personnel responsible for treatment dispensation, preparation, administration and accountability.

### **6.4 Efficacy**

All efficacy assessments should be performed prior to administration of study treatment. Qualified site personnel (efficacy assessors) other than those treating the subjects, blinded to the allocation, will perform the efficacy assessments.

There are two co-primary efficacy variables in this study: PASI 75 response and IGA mod 2011 0 or 1 response.

The following order should be applied when performing the efficacy assessments during study visits:

- Investigator's Global Assessment (IGA mod 2011; scale from 0 – 4)
- Psoriasis Area and Severity Index (PASI; score from 0 – 72)

#### **6.4.1 Investigator Global assessment (IGA mod 2011)**

An efficacy assessor other than the investigator treating the subject will perform IGA mod 2011 assessment as indicated in [Table 6-3](#). It is recommended that the same assessor conducts the efficacy assessment throughout the study whenever possible.

The IGA mod 2011 rating scale for overall psoriatic disease is shown in [Table 6-3](#) below.

The IGA mod 2011 scale has been developed based on a previous version of the scale used in secukinumab phase II studies in collaboration with health authorities, in particular the FDA.

The explanations/descriptions of the points on the scale have been improved to ensure appropriate differentiation between the points.

The IGA mod 2011 used in this study is static, i.e., it refers exclusively to the subject's disease state at the time of the assessments, and does not attempt a comparison with any of the subject's previous disease states, whether at baseline or at a previous visit.

The IGA mod 2011 score will be recorded in the eCRF.

**Table 6-3 IGA mod 2011 scale**

0	Clear, No signs of psoriasis. Post-inflammatory hyperpigmentation may be present
1	Almost clear- Normal to pink coloration of lesions; no thickening; no to minimal focal scaling
2	Mild- Pink to light red coloration; just detectable to mild thickening; predominantly fine scaling
3	Moderate -Dull bright red, clearly distinguishable erythema; clearly distinguishable to moderate thickening; moderate scaling
4	Severe- Bright to deep dark red coloration; severe thickening with hard edges; severe / coarse scaling covering almost all or all lesions

Based on this scale, a subject will be eligible to participate in the study if the subject has an IGA mod 2011 score at baseline of 4.

Based on this scale, a subject will be considered as IGA mod 2011 0 or 1 responder if the subject achieves a score of 0 or 1 and improved by at least 3 points on the IGA mod 2011 scale compared to baseline. The IGA score will be recorded in the study-specific paper source form then will be entered into the eCRF at all visits with exception of Randomization visit when it will be also entered into the IRT to assess eligibility based on IGA mod 2011 score.

#### **6.4.2 Assessment of total body surface area (BSA) and psoriasis area safety index (PASI)**

The efficacy assessor (other than the investigator treating the subject) will complete the PASI assessment as indicated in [Table 6-1](#), [Table 6-2](#). Whenever possible, the same assessor should perform this efficacy assessment at all visits.

The total BSA affected by plaque-type psoriasis will be estimated from the percentages of areas affected, including head, trunk, upper limbs and lower limbs (see below for full details of the PASI assessment). The following calculations will be done: Each reported percentage will be multiplied by its respective body region corresponding factor (head = 0.1, trunk = 0.3, upper limbs = 0.2, lower limbs = 0.4). The resulting four percentages will be added up to estimate the total BSA affected by plaque-type psoriasis.

A PASI score ([Fredriksson 1978](#), [Weisman 2003](#), [Gottlieb 2005](#)) will be derived as indicated in [Table 6-4](#). The head, trunk, upper limbs and lower limbs are assessed separately for erythema, thickening (plaque elevation, induration), and scaling (desquamation). The average degree of severity of each sign in each of the four body regions is assigned a score of 0-4. The area covered by lesions on each body region is estimated as a percentage of the total area of that particular body region. Further practical details help the assessment:

- The neck is assessed as part of the head.

- The axillae and groin are assessed as part of the trunk.
- The buttocks are assessed as part of the lower limbs.
- When scoring the severity of erythema, scales should not be removed.

**Table 6-4 PASI scoring system**

Body region	Erythema (E)	Thickening (I) (plaque elevation, induration)	Scaling (D) (desquamation)	Area score (A) (based on true area %)*
Head (H)†	0=none	0=none	0=none	0 = no involvement
	1=slight	1= slight	1= slight	1 = >0-<10%
	2= moderate	2= moderate	2= moderate	2 = 10-<30%
	3= severe	3= severe	3= severe	3 = 30-<50%
	4=very severe	4=very severe	4=very severe	4 = 50- <70%
				5 = 70-<90%
Trunk (T)‡	0=none	0=none	0=none	0 = no involvement
	1=slight	1= slight	1= slight	1 = >0-<10%
	2= moderate	2= moderate	2= moderate	2 = 10-<30%
	3= severe	3= severe	3= severe	3 = 30-<50%
	4=very severe	4=very severe	4=very severe	4 = 50- <70%
				5 = 70-<90%
Upper limbs (U)	0=none	0=none	0=none	0 = no involvement
	1=slight	1=slight	1=slight	1 = >0-<10%
	2=moderate	2=moderate	2=moderate	2 = 10-<30%
	3=severe	3=severe	3=severe	3 = 30-<50%
	4=very severe	4=very severe	4=very severe	4 = 50- <70%
				5 = 70-<90%
Lower limb (L)§	0=none	0=none	0=none	0 = no involvement
	1=slight	1=slight	1=slight	1 = >0-<10%
	2=moderate	2=moderate	2=moderate	2 = 10-<30%
	3=severe	3=severe	3=severe	3 = 30-<50%
	4=very severe	4=very severe	4=very severe	4 = 50- <70%
				5 = 70-<90%

\* Percentage (not score) of body region (not whole body) affected will be entered in the eCRF

† Neck is assessed as part of the Head (H) body region.

‡ Axillae and groin are assessed as part of the Trunk (T) body region.

§ Buttocks are assessed as part of the Lower limbs (L) body region.

Because the head and neck, upper limbs, trunk and lower limbs correspond to approximately 10%, 20%, 30% and 40% of the body surface area, respectively, the PASI score is calculated using the formula:

$$\text{PASI} = 0.1 (\text{EH} + \text{IH} + \text{DH})\text{AH} + 0.2(\text{EU} + \text{IU} + \text{DU})\text{AU} + 0.3(\text{ET} + \text{IT} + \text{DT})\text{AT} + 0.4(\text{EL} + \text{IL} + \text{DL})\text{AL}$$

The keys for the letters are provided in [Table 6-4](#).

PASI scores can range from a lowest value of 0, corresponding to no signs of psoriasis, up to a theoretic maximum of 72.

The efficacy assessor is responsible for evaluating the subject and collecting the components, scoring signs and total regional area. The efficacy assessor/qualified site staff will record PASI data in the study-specific paper source worksheet at study visits and subsequently, investigator/qualified site staff will enter the data into PASI eCRF.

Calculations based on collected PASI components (e.g. total PASI score, BSA, PASI 75 responder status- as applicable) will be done by efficacy assessor/qualified site staff. These will also be entered in the PASI source worksheet and PASI eCRF as required.

At Visit 1 and Visit 2, the efficacy assessor/qualified site staff, after collecting the components of the PASI calculation, must calculate and verify (as indicated previously) the total PASI score and the total BSA.

Based on PASI, to be eligible, a subject must have a score of 20 or more at the Randomization Visit.

Based on total BSA, to be eligible, a subject must have 10% or more total BSA involved at the Randomization Visit.

Only if the above eligibility criteria and all other eligibility criteria are fulfilled should site contact IRT at the Randomization Visit to randomize the subject.

At Visit 8 (Week 12), the efficacy assessor/qualified site staff, after collecting the components of the PASI calculation, must calculate (as indicated previously) the total PASI score. In addition the PASI 75 responder status of the subject must be calculated. Subjects achieving  $\geq 75\%$  improvement (reduction) in PASI score compared to baseline (Randomization Visit) are defined as **PASI 75 responders**. Those achieving  $< 75\%$  improvement are considered as PASI 75 non-responders. These will also be entered in the PASI source worksheet and PASI eCRF.

Once this is calculated and verified the site can contact IRT and indicate whether the subject is PASI 75 responder on PASI 75 non responder.

### **Definitions of efficacy variables based on PASI**

[figure not shown]
The following definitions are used in this study (see [CHMP guidelines for psoriasis \(CHMP/EWP/2454/02 2004\)](#)):

**PASI 50 response (partial response)**: subjects achieving  $\geq 50\%$  improvement (reduction) in PASI score compared to baseline are defined as PASI 50 responders

**PASI 75 response**: subjects achieving  $\geq 75\%$  improvement (reduction) in PASI score compared to baseline are defined as PASI 75 responders

**PASI 90 response**: subjects achieving  $\geq 90\%$  improvement (reduction) in PASI score compared to baseline are defined as PASI 90 responders

**PASI 100 response / remission**: complete clearing of psoriasis (PASI=0)

#### **6.4.4 Appropriateness of efficacy assessments**

The PASI score, the assessment of the severity of the psoriasis symptoms and the extent to which the subject's body area is affected by the disease, is considered acceptable by health authorities (CHMP guideline on the treatment of psoriasis-[CHMP/EWP/2454/02 2004](#)) to assess efficacy in conjunction with Investigator's Global Assessment (IGA).

### **6.5 Safety**

All blood draws and safety assessments should be done prior to study treatment administration. Appropriate safety assessments (e.g., evaluation of AEs and SAEs including injection site reactions) should be repeated after the dose is administered.

During the COVID-19 pandemic or similar major health care disruption that limits or prevents on-site study visits, phone calls, virtual contacts (e.g. teleconsult), or visits by site staff or home nursing service depending on local regulations and capabilities may occur on or around scheduled protocol visit dates (or more frequently if needed). This will be done for safety monitoring and discussion of the subject's health status until the subject can again visit the site. Case report forms (e.g. AEs, concomitant medications, procedures and non-drug therapies) should be updated as appropriate.

#### **6.5.1 Physical examination**

A physical examination, including general appearance, skin, neck, eyes, ears, nose, throat, lungs, heart, abdomen, back, lymph nodes, and extremities, and vascular and neurological systems will be performed as indicated in [Table 6-1](#), [Table 6-2](#). Investigator should pay special attention to any signs or symptoms of potential skin or mucosal candida infections.

If indicated, based on medical history and/or symptoms, additional exams will be performed at the discretion of the investigator.

If possible, assessments for an individual subject should be performed by the same member of the study site staff throughout the study.

Information for all physical examinations must be included in the source documentation at the study site. Significant findings that are present prior to the screening visit (Visit 1) must be included in the Medical History screen on the subject's eCRF. Significant findings made after

the start of study (Visit 1) that meet the definition of an adverse event must be recorded on the Adverse Event screen of the subject's eCRF.

### 6.5.3 Vital signs

Vital signs (including blood pressure and pulse measurements) will be assessed at every scheduled visit as indicated in [Table 6-1](#), [Table 6-2](#). If possible, assessments should be performed by the same study site staff member throughout the study.

After the subject has been sitting for five minutes, with back supported and both feet placed on the floor, systolic and diastolic **blood pressure will be measured twice** (measurements separated by 1 to 2 minutes) using a validated device, with a cuff that is appropriately sized for the subject's arm circumference. The average of the two measurements will be entered on the Vital Signs eCRF.

Whether action needs to be taken to address notable vital signs will be decided by the investigator/qualified site staff, taking into account the overall status of the subject. No specific action is foreseen as part of the study protocol. Notable values for vital signs are indicated in [Appendix 1, Table 13-1](#).

### 6.5.4 Height and weight

Height and body weight will be measured at visits as in [Table 6-1](#), [Table 6-2](#). Height measurements (in indoor clothing, but without shoes, socks, hats or hair accessories interfering with assessment) will be made using a stadiometer that is calibrated on a regular basis. Height measurements will be performed twice and the reported height will be the mean of the 2 measurements.

If possible, body weight assessments (in indoor clothing, but without shoes) should be performed by the same study site staff member and using the same scale throughout the study. The body weight recorded at Randomization (Visit 2) will be used to categorize the subject population at randomization and placebo PASI 75 non-responders at Week 12 respectively, to receive the corresponding doses in the high dose and low dose secukinumab groups.

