### **3      Investigational plan**

#### **3.1      Study design**

[figure not shown]
This is a multicenter, randomized, double-blind, placebo- and active-controlled (etanercept in single blinded arm) study in pediatric subjects aged 6 years to less than 18 years with severe chronic plaque psoriasis. Approximately 160 subjects aged 6 years to <18 years will be enrolled, of which at least 30 will be 6 years to <12 years old. It is expected that subjects will be enrolled at approximately 70 study sites worldwide.

Two age subgroups will be studied in a staggered approach within this clinical study: 12 to less than 18 years of age, and 6 to less than 12 years of age (age for the subgroups determined at the time of randomization). Enrolment of children aged 6 to less than 12 years will begin after a favorable recommendation by an independent external Data Monitoring Committee (DMC) who will review data of approximately 80 (approximately 40 treated with secukinumab) enrolled adolescents (aged 12 to less than 18 years) treated for 28 weeks. Adolescents will continue to be recruited while the data from the first 80 subjects are being collected and analyzed.

Subjects will be randomized using a 1:1:1:1 ratio into one of the treatment arms: secukinumab low dose, secukinumab high dose, etanercept or placebo. Subjects randomized to secukinumab treatment arms (high dose and low dose) will receive dose based on the weight category (<25 kg, 25 to <50kg,  $\geq$ 50 kg). If a subject moves into a higher or lower weight group at two consecutive visits with weight measurements during the maintenance (from Week 12 onwards as assessed at monthly visits, i.e. Week 13, 14, 15 will not be taken into account) or during extension treatment period (as assessed at scheduled site visits), the subject will receive dosing according to the new (higher or lower) weight group respectively.

**Figure 3-1** Study design

The study consists of 5 Epochs: screening (up to 4 weeks), induction (of 12 weeks), maintenance (of 40 weeks), extension treatment epoch (open-label of 184 weeks) and post-treatment follow-up epoch (of 16 weeks). An outline of the visits is presented in [Figure 3-1](#), while a detailed visit and assessment schedule can be found in [Table 6-1](#), [Table 6-2](#).

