#### **5.2 Treatment arms**

Subjects will be randomized using a 1:1:1:1 ratio into one of the treatment arms mentioned below. Subjects randomized to secukinumab treatment arms (high dose and low dose) will receive dose according to the weight category (<25 kg, 25- <50kg,  $\geq$ 50 kg). Subjects in the two secukinumab arms weighing  $\geq$ 50kg will receive 150 mg (low dose group) and 300 mg (high dose group), 25 to <50 kg will receive 75mg (low dose group) and 150 mg (high dose group) and <25kg will receive 75mg for both dose groups. In order to maintain the treatment blind, all subjects in secukinumab or placebo arms will receive 2 s.c. injections at each dose, except for subjects <25kg weight category who will receive only 1 injection of either 75 mg secukinumab or matching placebo ([Table 5-1](#)).

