**Table 5-1 Secukinumab/Placebo treatment arms and injections at each visit during Induction and maintenance epoch**

Weight category at randomization	Treatment arms	Blinded Dose (PFS)	Number of injections at each visit during Induction Epoch	Number of injections at each visit during Maintenance Epoch
<25 kg	AIN high dose	75mg/0.5mL AIN	1	1
	AIN low dose	75mg/ 0.5mL AIN	1	1
	Placebo high dose(pre assigned at randomization)	75mg/0.5mL AIN PBO	1	1*
	Placebo low dose (pre-assigned at randomization)	75mg/0.5mL AIN PBO	1	1*
25 to <50kg	AIN high dose	2x75mg/0.5mL AIN	2	2
	AIN low dose	75mg/0.5mL AIN +75mg/0.5mL AIN PBO	2	2
	Placebo high dose(pre assigned at randomization)	2x75mg/0.5mL AIN PBO	2	2*
	Placebo low dose (pre-assigned at randomization)	2x75mg/0.5mL AIN PBO	2	2*
≥50kg	AIN high dose	2x150mg/1.0ml AIN	2	2
	AIN low dose	150mg/1.0mL AIN+150mg/1.0mL AIN PBO	2	2
	Placebo high dose(pre assigned at randomization)	2x150mg/1.0mL AIN PBO	2	2*
	Placebo low dose (pre-assigned at randomization)	2x150mg/1.0 mL AIN PBO	2	2*

\*Placebo PASI 75 non responders will start receiving at Week 12 active treatment (secukinumab) high or low, as preassigned at randomization

- **Etanercept active comparator group:** S.C. etanercept 0.8 mg/kg (up to a maximum dose of 50 mg) once per week, for 51 weeks administered at home (self-injected or by caregiver) or at the study site. No subject blinding will be introduced for this arm, but the efficacy assessor will be blinded as regards to treatment assignment.
- **Secukinumab low dose group:** According to the weight category, s.c. secukinumab 75 mg (in <25 kg and 25 to <50 kg) or 150 mg (≥50 kg) injections at Randomization, Weeks 1, 2, 3, 4, 8, 12, 16, 20, 24, 28, 32, 36, 40, 44, and 48, and Placebo secukinumab at Weeks 13, 14 and 15 during the blinded phase of the study; thereafter at Week 52 and every 4 weeks during the extension treatment epoch until Week 232. Subjects and all site staff will be blinded as regards to treatment assignment and secukinumab dose levels during the induction and maintenance epochs. After data base lock for Week 52

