  - **PASI 75 non-responders on placebo** will receive high dose or low dose secukinumab, according to the pre-assignment at the Randomization visit, and receive their treatment according to the weight category based on the weight measured at Week 12 visit (<25 kg, 25- <50kg,  $\geq$ 50 kg), on Weeks 12, 13, 14, 15, and then every four weeks starting at Week 16 until Week 48 during the maintenance epoch; thereafter Week 52 and every 4 weeks during the extension treatment epoch until week 232. After data base lock for Week 52 analysis has been performed, the placebo injection will no longer be administered and the study will become open label. In the extension treatment epoch, between the site visits, subjects will be expected to perform the study treatment administrations at home. This can be self-administered by subject or by caregiver. Subjects <12years of age must not self-administer. However, adolescents (aged 12 to  $\leq$ 18 years) can self-administer while under supervision of HCPs or caregiver/guardian. If

subject/parent do not feel confident in performing treatment administration at home they are still allowed to receive study treatment administration at site.

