#### **Stratification**

Randomization will be stratified by age and body weight collected at Randomization Visit. This stratification ensures balanced allocation of subjects to treatment groups within the age and weight strata.

The age strata is “age < 12” or “age  $\geq$  12”. The weight strata will be “body weight < 25 kg”, “25 kg  $\leq$  body weight < 50 kg” or “body weight  $\geq$  50 kg”. Stratification by age and body weight will occur at Randomization Visit. For the randomization at Randomization Visit, it will be targeted to have at least approximately 30% of the subjects in each weight stratum.

The randomization scheme for subjects will be reviewed and approved by a member of the IQS Randomization Group.

Within each weight stratum, subjects will be assigned to the high dose or the low dose treatment group for secukinumab or placebo (see [Table 5-1](#)).

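### Protocol 6.5.4 sets the Week 12 dose category of placebo non-responders by Randomization weight, but 5.2 sets it by Week 12 weight (minor; words probably dropped)

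*Protocol*

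**What the plan says.** Two sections of the protocol tell the reader which weight sets the dose when a placebo PASI 75 non-responder starts secukinumab at Week 12.

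- **Section 6.5.4 (Height and weight)** names one weight, the one "recorded at Randomization (Visit 2) will be used to categorize the subject population at randomization and placebo PASI 75 non-responders at Week 12 respectively", and says this is for assigning the corresponding high-dose or low-dose group doses.
- **Section 5.2 (Treatment arms, Placebo group)** says these children "receive their treatment according to the weight category based on the weight measured at Week 12 visit".

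Table 5-1 heads its rows "Weight category at randomization". Its last column is "Number of injections at each visit during Maintenance Epoch", with starred entries for the placebo rows. The footnote to those entries reads: "Placebo PASI 75 non responders will start receiving at Week 12 active treatment (secukinumab) high or low, as preassigned at randomization".

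Section 3.1 covers later changes of weight category. A child is re-dosed after being in a new category at two consecutive visits with a weight measurement, "from Week 12 onwards as assessed at monthly visits, i.e. Week 13, 14, 15 will not be taken into account".

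**The concern.** A placebo child who crosses a weight threshold between Randomization and Week 12 has two different category assignments, depending on which section is read. The weight category determines the milligram dose, and Section 3.6 presents weight-based dosing as the means of keeping exposure comparable across weights. The conflict therefore concerns the dose a child receives. Someone who relied on 6.5.4 could find apparent support in the Table 5-1 row heading.

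**Working it through.** There is no sample size, power or error-rate figure to reproduce. The check compares the texts, reads the dose difference from 5.2, and then illustrates how many children could be involved.

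**1. Can the texts be reconciled?** Section 6.5.4 lists two occasions (randomization, and Week 12 for switchers) and ends with 'respectively', but names only one weight. That fits a dropped reference to the Week 12 visit, which would make it agree with 5.2. As printed, it does not agree.

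Table 5-1 does not settle the matter. Its maintenance column counts injections, its placebo rows list only placebo syringes, and its footnote fixes only high or low. The only mismatch with 5.2 is the row heading, and through it the starred injection counts (1 below 25 kg, 2 above).

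**2. Dose difference per injection day, from 5.2 (below versus above the threshold).**

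| Threshold crossed | Dose group | Below | Above | Ratio |
|---|---|---|---|---|
| 25 kg | Low | 75 mg | 75 mg | 1 |
| 25 kg | High | 75 mg | 150 mg | 2 |
| 50 kg | Low | 75 mg | 150 mg | 2 |
| 50 kg | High | 150 mg | 300 mg | 2 |

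The first row shows no difference because "<25kg will receive 75mg for both dose groups".

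**3. How long the difference can last.** Switched children receive active drug at Weeks 12, 13, 14 and 15, then every four weeks from Week 16. Under 3.1 the first two qualifying weights are at Weeks 12 and 16, so the dose can be re-aligned at Week 16 at the earliest. Four doses are exposed:

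- 4 × 75 = 300 mg versus 4 × 150 = 600 mg; or
- 4 × 150 = 600 mg versus 4 × 300 = 1200 mg.

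**4. How many children (illustration).**

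*From the documents:* 160 children randomized 1:1:1:1; an assumed placebo PASI 75 rate of 10% (Section 9.7); and, for the weight strata, "it will be targeted to have at least approximately 30% of the subjects in each weight stratum" (Section 5.3).

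*Assumed here:* 30% of switchers in each of the two lower strata; weights spread evenly within a stratum; the <25 kg stratum 5 to 10 kg wide; half pre-assigned to high dose; a gain of 0.5 to 1.5 kg in 12 weeks.

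- Switchers: 160/4 × 0.90 = 36.
- Per lower stratum: 36 × 0.30 = 10.8.
- Crossing 50 kg: 10.8/25 = 0.432 per kg; × 0.5 to 1.5 kg = 0.22 to 0.65.
- Crossing 25 kg, high-dose half, stratum 10 kg wide: 10.8/10 × 0.5 = 0.54 per kg, giving 0.27 to 0.81.
- Crossing 25 kg, high-dose half, stratum 5 kg wide: 10.8/5 × 0.5 = 1.08 per kg, giving 0.54 to 1.62.
- Total: 0.22 + 0.27 = 0.49 at the low end; 0.65 + 1.62 = 2.27 at the high end.
- As a share of 36: 1.4% to 6.3%.

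**5. Does it touch the analysis?** Section 3.1 places the Week 12 assessments before the Week 12 dose, so PASI 75, IGA 0 or 1 and PASI 90 at Week 12 are unaffected. The body-weight-by-dose groups in SAP 4.1 are made up of patients randomized to secukinumab, so switched placebo children are not in them.

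**The case against.** The strongest reply is that this is an editorial slip that any careful reader can resolve. Section 5.2 is the section that governs dosing and it is explicit, whereas 6.5.4 mainly describes measurement, and its stray 'respectively' signals the omission. Sites do not choose the dose from 6.5.4 either. IRT allocates the medication (Section 5.5.2) and receives the weight measured at each visit (Table 6-1, footnote 14), so the Week 12 weight was available at the switch. Section 3.1 already accepts a similar lag for secukinumab-arm children who cross a threshold during induction. The Table 5-1 heading is only a label. The count of children rests mostly on assumptions: 1.62 of the 2.27 upper figure comes from the 25 kg term. Finally, the last Week 24 visit was 7 March 2019 (SAP 2.15.5) and Amendment 4 is dated 18 September 2020, so rewording changes no child's dose.

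Most of this stands, and it is why the point is minor. It does not remove the contradiction. Section 6.5.4 says in terms that the weight is used to assign doses, and the IRT specification, which would show which rule was programmed, is not in the documents. SAP 4.1 records a different IRT error in these same weeks, in which 36 patients in the secukinumab groups were dispensed active drug at Weeks 13 to 15 (the match with the 36 switchers above is coincidence). That is not evidence of a weight-rule error, but it is a reason to check the records rather than assume they are right.

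**Conclusion.** The concern holds. Section 6.5.4 is wrong as written and conflicts with 5.2; 5.2 is very probably the intended rule. The possible consequence is a two-fold dose difference over at most four doses if 3.1 re-aligns the dose at Week 16. It is limited to switched placebo children who crossed 50 kg (either dose group) or 25 kg (high-dose group only) during induction.

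The documents do not report how many children did so. The figure of about 0.5 to 2.3 depends on the assumed weight gain, stratum width and even spread of weights, and the true number may be zero. No misdosing is shown, and the co-primary and key secondary comparisons are untouched. Severity: minor.

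**What to change.** 1. In 6.5.4, insert 'and at Week 12 (Visit 8)' after the reference to Randomization (Visit 2), so that 'respectively' has two weights to refer to and the section agrees with 5.2.
2. Add a footnote to Table 5-1 saying that the starred maintenance entries follow the Week 12 weight category.
3. Because all switches are complete, check in the IRT and dispensing records which weight was used for each switched placebo child.
4. Add any switched child whose Randomization and Week 12 categories differ to the listing that SAP 2.5.1 already plans for subjects whose dose changed with weight group. As described, that listing could miss such a child, because there is no earlier secukinumab dose to change from.

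Section 3.1 needs no change. The cost is a few words, one footnote, one records check and possibly a few extra rows in an existing listing. Trial conduct and the planned efficacy analyses stay as they are.
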